### **10.3.1 Temporary treatment discontinuation with investigational medicinal product(s)**

Re-initiation of treatment with the IMP will be done under close and appropriate clinical/and or laboratory monitoring once the Investigator will have considered according to his/her best medical judgment that the responsibility of the IMP in the occurrence of the concerned event was unlikely and if the selection criteria for the study are still met (see [Section 6.2](#) and [Section 6.3](#)).

All temporary treatment discontinuation and date of treatment re-initiation should be recorded by the Investigator in the appropriate pages when considered as confirmed.

### **10.3.2 Definitive treatment discontinuation with investigational medicinal product(s)**

All patients who prematurely and permanently discontinue study medication will be asked to continue until the planned end of the double-blind treatment period EPTD. After completion of the premature discontinuation visit (EOT) and the post drug elimination follow-up visits, the patients continue to have study visits approximately every 12 weeks for clinical follow-up including EDSS, relapse reporting, AE reporting and Concomitant Medications recording.

In a specific emergency, participants who are close to the end of treatment may be unable to continue their final treatment as scheduled. These patients would be considered to have permanently discontinued their treatment ([Section 17.7](#)).

#### **10.3.2.1 List of criteria for definitive treatment discontinuation**

The patients discontinue from study treatment if the patients/parents/guardians decide to do so, at any time and irrespective of the reason or the investigator may decide that it is best for the patient to stop treatment.

Study medication will be discontinued and the washout procedure will be performed after any of the following events:

#### **Safety**

- If acute, potentially life-threatening cytopenias develop.
- If severe bullous skin reactions develop. As soon as skin or mucosal reactions are observed which raise the suspicion of such severe reactions.
- A SGPT/ALT >3-fold ULN must be repeated within 48 hours. In the event of a confirmed value of >3- fold ULN, study medication should be discontinued and subject monitored until the value normalizes.

- A SGPT/ALT between 2 and 3-fold ULN associated with any of the following signs and symptoms including fever, rash, abdominal pain, dark urine, light stools.
- A serum amylase and/or lipase >2-fold ULN associated with symptoms consistent with pancreatitis (eg, abdominal pain, back pain, nausea and vomiting, fever, sweating) or serum amylase and/or lipase >5-fold ULN with or without associated symptoms.
- Abdominal CT scan or MRI findings consistent with chronic pancreatitis. A washout procedure will be initiated following discontinuation.
- If a drug-related peripheral neuropathy is diagnosed.
- If pulmonary toxicity is diagnosed.
- If a patient is found to be HIV positive.

#### **Other**

- If a female patient becomes pregnant or wishes to become pregnant during the study (if a female patient confirms plans to continue the pregnancy).
- If a male patient wishes to father a child during the study.

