### 6.3.4 Criteria to reduce reproductive risk

The effect of teriflunomide on human fetal development is not known, and may be potentially harmful based on results from animal studies. Therefore, all patients must be fully informed as to this risk and provide written consent /assent to not become pregnant or father a child during their participation in this study. If during the study, a female patient becomes pregnant or decides to attempt to become pregnant or if a male patient decides to attempt to father a child, then she or he must stop the study medication and undergo the accelerated elimination procedure.

Female patients must not be breast feeding or pregnant (as confirmed by serum pregnancy test) at the time of study entry and must agree to undergo serum pregnancy testing throughout the study at each 12-week clinic visit. In addition, pregnancy test should be conducted in case of an unexpected delay of menstruation.

Definition of “woman not of child bearing potential”:

- Be sterilized (eg, hysterectomy, bilateral oophorectomy, bilateral salpingectomy or bilateral tubal ligation).

A woman of child bearing potential (WOCBP) is any female who has experienced menarche and does not meet the criteria for “woman not of child bearing potential”.

Women of child bearing potential and male subjects must agree that they will take means to reduce reproductive risk by agreeing to use a double method of contraception (ie, an acceptable method in both female and male) until successful plasma elimination has been confirmed (refer to [Section 9.9](#)). Acceptable methods of contraception are defined for this protocol as:

- For male:
  - True abstinence: when this is in line with the preferred and usual lifestyle of the subject (Periodic abstinence [eg, calendar, ovulation, symptothermal, post ovulation methods] and withdrawal are not acceptable methods of contraception),
  - Male sterilization (with the appropriate post vasectomy documentation of the absence of sperm in the ejaculate),
  - Use of condoms throughout the study, in addition to spermicides is recommended.
- For women of child bearing potential:
  - True abstinence: when this is in line with the preferred and usual lifestyle of the subject (periodic abstinence [eg, calendar, ovulation, symptothermal, post ovulation methods] and withdrawal are not acceptable methods of contraception),

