### 9.3 PHYSICAL EXAMINATION

Physical examinations are performed at screening, baseline, every 12 weeks thereafter and at EOT. In addition, one examination is also performed at the first post drug elimination follow up visit. Physical examinations should be performed for patients who prematurely discontinued the study treatment.

The Tanner scale (also known as the Tanner stages I-V) is a scale of physical development in children, adolescents and adults (Marshall and Tanner, 1969; Marshall and Tanner, 1970). The scale defines physical measurements of development based on external primary and secondary sex characteristics, such as the size of the breasts, genitalia, and development of pubic hair.

Tanner scale is performed either at the study site by the pediatric neurologist or pediatrician or at a designated site arranged by the investigator. Tanner scale is encouraged to be performed at scheduled visits. However, it is acceptable if the assessments are performed shortly after the scheduled visits due to logistical reasons.

The treating neurologist must assess for neurological signs and symptoms suggestive of a peripheral neuropathy (defined as bilateral sensory and/or motor involvement with stocking glove distribution) at each visit involving a physical examination. If the treating neurologist suspects a peripheral neuropathy then electrophysiological nerve conduction studies must be performed. If the overall assessment of the patient is consistent with a diagnosis of peripheral neuropathy or the worsening of a pre-existing peripheral neuropathy, that event will be reported as AE. If a drug-related peripheral neuropathy is suspected treatment should be discontinued ([Section 1.3](#), [Section 1.4](#), [Section 1.5](#)).

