- Pulmonary symptoms such as onset or worsening of cough or dyspnea requiring pulmonary evaluation and consistent with a pulmonary toxicity.
- Peripheral neuropathy confirmed by nerve conduction study.  
All neurological symptoms suggestive of a peripheral neuropathy will be followed up with nerve conduction studies.
- Any sign, symptom, laboratory data suggestive or evocative of renal dysfunction with acute renal failure, as defined by a rapid increase in serum creatinine over 150  $\mu$ mol/L or rapid decrease in creatinine clearance below 50ml/min (See 17.4 for guidance of reporting and Follow-Up).
- Severe skin reaction such as toxic epidermal necrolysis or Stevens Johnson syndrome.
- Sustained increase in blood pressure: SBP  $\geq$ 160 mmHg, DBP  $\geq$ 100 mmHg on at least 2 consecutive visits.
- Other reasons for expedited reporting:
  - Overdose (see Section 9.8.4). An overdose (symptomatic or not) with the IMP is an event suspected by the Investigator or spontaneously notified by the patient and defined as at least twice the intended dose (ie, 2 tablets) on a given calendar day. The circumstances (ie, accidental or intentional) should be clearly specified in the verbatim and symptoms, if any, entered on separate AE form,

- Any pregnancy diagnosed in a female subject or in the female partner of a male subject during treatment with the IMP must be reported to the Sponsor immediately. The treatment should be withdrawn and the accelerated elimination procedure performed. Information related to the pregnancy must be provided to the Sponsor. Information related to the birth of a child of an exposed patient must be provided to the Sponsor. The “Drug exposure via parent” form must be completed.

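### The pregnancy stopping rule is conditional in the list of definitive discontinuation criteria (10.3.2.1) but unconditional in 6.3.4 and 9.8.1; partner pregnancy and the neuropathy trigger are also not aligned

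*Protocol*

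**What the plan says.** Three places in the protocol set a stopping rule for pregnancy.

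- Section 6.3.4 (reproductive risk) is triggered when, during the study, "a female patient becomes pregnant or decides to attempt to become pregnant", or when a male patient decides to try to father a child. The action is "then she or he must stop the study medication and undergo the accelerated elimination procedure".
- Section 9.8.1 (events for specific reporting) is triggered by "Any pregnancy diagnosed in a female subject or in the female partner of a male subject during treatment with the IMP". The action is "The treatment should be withdrawn and the accelerated elimination procedure performed".
- Section 10.3.2.1 (criteria for definitive discontinuation, under Other) reads "If a female patient becomes pregnant or wishes to become pregnant during the study (if a female patient confirms plans to continue the pregnancy", where the bracket closes. For male patients it reads "If a male patient wishes to father a child during the study".

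Two places set a rule for peripheral neuropathy.

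- Section 9.3 (physical examination): "If a drug-related peripheral neuropathy is suspected treatment should be discontinued".
- Section 10.3.2.1 (under Safety): "If a drug-related peripheral neuropathy is diagnosed".

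The lead-in to the 10.3.2.1 list makes both stopping and washout mandatory after any listed event. It does not say that these are the only grounds. Just before it, the same section lets the investigator stop treatment for any patient. No cross-reference or order of precedence links the five statements.

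**The concern.** Section 10.3.2.1 is by its title the place to look up whether a patient must stop for good, and it also governs washout. If its pregnancy criterion is narrower than the instruction given in two other sections, sites have two mandatory texts that give different answers for the same patient.

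The protocol itself names the hazard. It reports embryofetal toxicity in rats and rabbits (3.1.2.2), treats harm to the human fetus as possible (6.3.4), and states that without accelerated elimination plasma levels can take years to fall to the accepted threshold (9.9).

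The rule is still in use. Amended protocol 05 is written for patients in the open-label and optional extension periods, and pubescent females have a serum pregnancy test every 12 weeks in the open-label period (flow chart footnotes, 1.4). About 100 sites were planned.

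**Working it through.** No arithmetic underlies this point, and there is no figure in the plan to reproduce. The check is to take each situation that can arise and read it against each section.

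**Pregnancy**

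| Situation | 6.3.4 | 9.8.1 | 10.3.2.1 |
|---|---|---|---|
| Patient pregnant, confirms she will continue | stop and eliminate | stop and eliminate | criterion met |
| Patient pregnant, undecided | stop and eliminate | stop and eliminate | criterion not met as qualified |
| Patient pregnant, does not plan to continue | stop and eliminate | stop and eliminate | criterion not met as qualified |
| Male patient's partner pregnant | not addressed (covers a decision to try) | stop and eliminate | not listed (covers a wish only) |

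The sections agree in one of the four rows.

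The bracket in 10.3.2.1 cannot be read as attaching to the wish to become pregnant, because it speaks of continuing a pregnancy, which presupposes that one exists. So it either restricts the criterion for an existing pregnancy, which gives rows two and three, or has no function. The text does not say which. Nor does it set a time by which a decision must be made.

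**Peripheral neuropathy**

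The paragraph in 9.3 runs in this order: the treating neurologist looks for signs; on suspicion, nerve conduction studies are required; if the overall assessment fits the diagnosis, an adverse event is reported; then comes the sentence on stopping when a drug-related neuropathy is suspected. That sentence can be read in three ways.

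1. Neuropathy itself is suspected and work-up is pending, and the stop is definitive. This conflicts with 10.3.2.1, which waits for a diagnosis.
2. Neuropathy is already diagnosed and the suspicion concerns drug causation. This is close to 10.3.2.1.
3. The stop on suspicion is temporary, as 10.3 allows for suspected adverse events, and becomes definitive on diagnosis. This is compatible with 10.3.2.1.

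The skin-reaction criterion in 10.3.2.1 refers expressly to suspicion, so the list can use that trigger when it means to. This makes the choice of *diagnosed* for neuropathy look deliberate, but it does not settle what 9.3 means. The neuropathy wording is therefore ambiguous; a contradiction is not established.

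**The case against.** The strongest reply is that the protocol should be read as a whole. The 10.3.2.1 list does not claim to be exhaustive, so failing its criterion does not cancel the instructions in 6.3.4 and 9.8.1. A site must use 9.8.1 to report a pregnancy, because immediate reporting to the sponsor and the withdrawal instruction stand in the same bullet. A patient who has been stopped could not restart while pregnant, since 10.3.1 requires the selection criteria still to be met and pregnancy is exclusion criterion E 16. The investigator may also stop anyone.

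Most of this stands, and it limits the point. A reader might infer that 10.3.2.1 keeps an undecided patient on drug, possibly without limit. The documents do not support that: no section instructs continued dosing, and such exposure would require a site to disregard two other sections. What the reply does not remove is that the definitive list states a condition which the other two sections lack, with nothing to say which prevails. Investigator discretion does not reconcile mandatory texts; it leaves the answer to vary between sites.

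A reader might also infer that the mismatch alters discontinuation and censoring in the double-blind primary analysis. That cannot be fixed by amendment now. The rationale for amended protocol 3, dated 02 August 2018, says enrolment was complete. Even a patient randomised on that date would reach Week 96 (96 × 7 = 672 days) on 4 June 2020, before the present version of 10 December 2020. The documents give no frequency for either event from which to argue an effect on counts.

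**Conclusion.** The pregnancy inconsistency is confirmed in current protocol text: conditional in 10.3.2.1, unconditional in 6.3.4 and 9.8.1. The omission of partner pregnancy from 10.3.2.1, against its inclusion in 9.8.1, is also confirmed. The neuropathy wording is a lesser matter: 9.3 does not say whether it means suspected drug causation, a temporary stop or a definitive one, so its relation to 10.3.2.1 is unclear.

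The size cannot be put as a number of patients, because the documents give no rates. It is best described as the set of situations without a single answer: three of the four pregnancy rows above, and a neuropathy that is suspected but not yet diagnosed. The case rests on clear safety instructions in the open-label and optional extension periods. It does not rest on the double-blind primary endpoint or its censoring, nor on any claim that the protocol directs treatment to continue. It assumes that the bracket in 10.3.2.1 was meant to have effect; if it was not, it is misleading and still needs correcting. Which clinical rule is right is not for this review to say.

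**What to change.** - Reconcile 6.3.4, 9.8.1 and 10.3.2.1 so that pregnancy has one trigger, worded identically in each place, and so that pregnancy in a male patient's partner is handled the same way throughout. The medical team decides which wording stands.
- Clarify in 9.3 what is suspected (the neuropathy or its drug causation) and whether the stop is temporary or definitive, and state how this relates to the criterion in 10.3.2.1.
- Add cross-references to 10.3.2.1 only after its wording is settled. Pointing 6.3.4 and 9.8.1 to the list as it stands could carry the disputed condition into sections that do not have it.

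The cost is wording in the next amendment and a memo to sites. No new procedures, data collection or analyses are needed.

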#### **10.3.2.2 Handling of patients after definitive treatment discontinuation**

Patients will be followed up according to the study procedures up to the scheduled date of study completion (96 weeks from randomization), or up to recovery or stabilization of a followed-up AE, whichever comes last.

If possible, all patients who prematurely and permanently discontinue study medication will be asked to perform EOT visit procedures and will be scheduled for post drug elimination visits. Wash-out medications should be prescribed (Cholestyramine or Activated charcoal, see [Section 9.9](#)). All definitive treatment discontinuation should be recorded by the Investigator in the appropriate eCRF pages when considered as confirmed.

#### **10.3.3 Procedure for withdrawal of patients from study follow-up schedule**

The patients may withdraw from the study if they decide to do so, at any time and irrespective of the reason.

All study withdrawals should be recorded by the Investigator in the appropriate eCRF pages when considered as confirmed;

For patients who fail to return to the site, the Investigator should make the best effort to re-contact the patient (eg, contacting patient's family or private physician, review available registries or health care database), and to determine his/her health status, including at least his/her vital status. Attempts to contact such patients must be documented in the patient's records (eg, times and dates of attempted telephone contact, receipt for sending a registered letter).

Patients who did not complete the study and for whom no end-of-treatment data are available will be considered as lost to follow-up.

## 11 STATISTICAL CONSIDERATIONS

The data from the placebo-controlled and the open label teriflunomide treatment phases will be the focus of the CSR of their respective phase. The following statistical methods/considerations relate to the analysis of the data from the placebo-controlled period. The data from the open label teriflunomide treatment arm are non-controlled and supportive in nature; summary statistics will be provided for each of the efficacy variables and safety data. For the optional additional extension period for young patients, the efficacy and safety data will be summarized by descriptive statistics and reported separately.

### 11.1 DETERMINATION OF SAMPLE SIZE

The sample size calculation is based on the primary efficacy endpoint, time to first confirmed relapse after randomization. Assuming 60% of placebo patients will experience a relapse by 2 years, 165 children aged 10 to <18 years (110 teriflunomide and 55 placebo; including approximately 20% pre-pubertal patients or 10% of patients under the age of 13 years at time of inclusion into the study and at least 25% male patients) are needed for 80% power to detect a hazard ratio (teriflunomide versus placebo) of 0.5 (2-sided alpha 0.05). The 2-year rate of relapse in the teriflunomide group would be 36.8% and the corresponding hazard rates, assuming the time-to-relapse is exponentially distributed with a constant hazard rate, would be 0.4581 for placebo and 0.2291 for teriflunomide. The sample size is adjusted assuming 20% of patients discontinue the study in 2 years due to reasons other than relapse. Calculations are performed using nQuery Advisor 7.

The assumption for the percentage of placebo patients with relapse at 2 years is based on the combined data from the completed Phase III monotherapy adult studies (EFC6049/TEMPO and EFC10531/TOWER), where 58.7% of placebo patients aged  $\leq 30$  (n=167) experienced at least 1 relapse in a 2-year treatment period. Of note, the corresponding percentage was 38.7% in the 163 patients aged  $\leq 30$  treated with teriflunomide 14 mg.

### 11.2 DISPOSITION OF PATIENTS

Screened patients are defined as any patient who met the inclusion criteria and where signed informed consent/assent was obtained from the patient and patient's legal representative (parents or guardians) according to local regulations.

Randomized patients consist of all patients, who have been allocated a treatment kit through the study randomization process, ie, with a treatment kit number allocated and recorded in the IVRS/IWRS database, regardless of whether the treatment kit was used or not.

Patients treated without being randomized will not be considered as randomized and will not be included in any efficacy population. Their safety experience will be reported separately, and these patients will not be in the safety population.

For any patient randomized more than once, only the data associated with the first randomization will be used in any analysis population. The safety experience associated with any later randomization will be assessed separately.

### **11.3 ANALYSIS POPULATIONS**

The randomized population includes any patient who has been allocated to a randomized treatment regardless of whether the treatment kit was used or not.

#### **11.3.1 Efficacy populations**

##### ***11.3.1.1 Intent-to-treat (ITT) population***

The analysis population for efficacy endpoints will be the ITT population, defined as all randomized patients who receive at least 1 dose of study medication, analyzed according to the treatment allocated by randomization.

##### **11.3.2 Safety population**

The analysis population for safety endpoints will be the safety population, defined as all randomized patients exposed to study medication, regardless of the amount of treatment administered. The safety analyses will be conducted according to the treatment patients actually received.

In addition:

- Nonrandomized but treated patients will not be part of the safety population, but their safety data will be presented separately.
- Randomized patients for whom it is unclear whether they took the study medication will be included in the safety population as randomized.
- For patients receiving both study medications during the trial, the treatment group allocation for as-treated analysis will be teriflunomide treatment.

##### **11.3.3 Pharmacokinetic population**

The PK population is a subset of the safety population containing patients who have at least one PK sample taken. Patients will be analyzed in the treatment group corresponding to the treatment actually received as defined for the safety population.

## **11.4 STATISTICAL METHODS**

### **11.4.1 Extent of study treatment exposure and compliance**

The extent of study treatment exposure and compliance will be assessed and summarized by actual treatment received within the safety population.

